Screening/Eligibility: During screening, eligibility will be determined using scripted questions: Inclusion/Exclusion Criteria. Potential subjects will be invited to participate in the study, demographics will be recorded. **Inclusion Criteria:** Postmenopausal women with clinically diagnosed vulvovaginal atrophy, age ≥ 55 years old and a screening vaginal pH of ≥ 5 , without menses for ≥ 12 months, no uterovaginal or vaginal vault prolapse beyond the hymen. **Exclusionary Criteria:** 1) Patients with BMI $\geq 35\text{kg}/\text{m}^2$. 2) Any patients with infections requiring antibiotic or antifungal therapy during the study period or within the last month or during the study period. 3) Study patients may not use any vaginal suppositories, douches, or vaginal hygiene wipes within the month preceding enrollment. 4) Patients receiving ongoing hormone replacement therapy. Patients already on hormone therapy, will be allowed to undergo a "wash out" period of estrogen or progesterone products for one month prior to enrollment. 5) Patients requiring concurrent use of steroid creams for other indications (e.g. lichen sclerosis). 6) Additional exclusions included patients with systemic conditions requiring immunosuppressive drugs, currently receiving chemotherapy, or history of pelvic radiation. 7) Any patients with contraindications to vaginal estrogen therapy including vaginal bleeding of unknown etiology. 8) Any patients with history of connective tissue disease. 9) Current tobacco use.

D.2. Study Design

The intention of this study is for each of the subjects to serve as her own control. Twenty patients will receive the treatment intervention. Five will not receive the treatment intervention. The five subjects not receiving

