Approach: The vaginal microbiome will be analyzed using 16S rRNA gene sequencing techniques evaluating specimens of mid-vaginal secretions to compare samples from each subject prior to initiation of vaginal estrogen cream and then again after eight weeks of therapy. This will yield 50 vaginal specimens in total for this specific aim (V1 = 25, V2 = 25; Treatment Group V1 = 20 vs. V2 = 20; Control Group V1 = 5 vs. V2 = 5). Baseline characteristics will be recorded and compared among the total cohort to identify covariates for adjusted analyses. Whole genome DNA (gDNA) will be extracted from specimens using DNA extraction kits (Zymo Research Corp, Irvine, CA) and PCR primers targeting the V4 rRNA gene will be used to prepare an amplicon library sequenced by the MiSeq platform (Illumina: San Diego, CA) and analyzed using the Quantitative Insight into Microbial Ecology (QIIME) suite. These raw data sequences will then be cross-validated and additional quality control measure will be applied. Analysis using QIIME will be supplemented with the use of the program DADA2 for more robust methods of sequence read de-noising and clustering to yield a higher degree of species-level identification (28). To better detect species of organisms known to be present in vaginal samples, taxonomy will be assigned using appropriately modified and validated databases (29-31).

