Based on these results, we expect the relative abundance of Lactobacillus in our cohort to be somewhere between 0.112-0.532 at baseline. As the selection criteria of our cohort does not include VVA symptomatology, we expect the relative abundance of Lactobacillus spp to be approximately 0.4 ± 0.3 . **With a Type-1 error of 0.05, we estimate with 80% power that we can detect an effect size of 0.2 increase (0.4→0.6) in the relative abundance of Lactobacillus spp with a treatment sample size of 20 patients.**

Biostatistical Analysis Plan: The following microbial community-level analyses will be performed to investigate the overall microbiome differences between the pre-treatment and post-treatments groups using the R package **phyloseq** (Table 2)(32).

Table 2. Overview of Community-Level Microbiome Analysis

Outcome	Measurements	Two-group comparisons
Alpha diversity (diversity within a sample)	Shannon, Chao, Simpson indices	t-tests, Mann-Whitney U
Beta diversity (diversity between samples, overall microbiota composition)	Bray-Curtis, unweighted UniFrac, weighted UniFrac (represented by PCoA to visualize clustering)	PERMANOVA or Dirichlet-multinomial distribution with Wald-type test

To identify individual taxa significantly associated with vaginal estrogen treatment, taxa-specific analyses will be performed. Given the distinct properties of microbiome data (compositional counts/proportions, varying total sequence reads across samples, over-dispersion), microbiome counts, transformations of microbiome counts, and beta regression for relative abundance will be used (33-39). To deal with zero-inflation of microbiome data, we will employ zero-inflated models: negative binomial (for count data), Gaussian (for logarithm or arcsine square root transformations), beta regression (for relative abundance) – which allow analysis of multiple covariates which may vary between treatment and non-treatment groups (38, 40-43). An R package *bmzim* for these models will be used. Standard procedures (e.g. Holm's, Hochberg's, Hommel's, Benjamini and Hochberg's methods) will be used to calculate p-values adjusted for multiple comparisons.

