Biostatistical Analysis Plan: Mean inflammatory marker concentrations and VMI scores will be compared by Student t-test or robust non-parametric tests between pre- and post-treatment samples. Normal linear regression will also be used to test the difference of the two cohorts (cytokine concentrations as response, cohort indicator as covariate). Similar methods will be used to analyze the difference in cytokine levels from V1 and V2 between groups. We will use three methods to investigate the relationship between bacterial taxa and cytokine levels: 1) Pearson's correlation coefficients will be calculated between cytokine levels and bacteria taxa (measured by percentage of reads) with a heat map showing correlations that are significantly different between pre- and post-treatment groups. To determine if cytokine levels and microbiota contribute to the clustering of women pre- and post-treatment, PCoA will be used to determine if these groups separate in space. Clusters will be examined for potential novel subsets of samples - with clinical data used to identify the cause of the clustering with linear and discrete data methods. 2) We will treat counts of each taxa as response, inflammatory cytokine levels as covariates and use negative binomial models (or zero-inflated versions). 3) We will treat cytokine levels as response, relative abundance of each taxa as covariates and use linear models. In these regressions, a pre-treatment indicator and an interaction term between pre-treatment and the covariates will be included. Similar methods will be used to analyze VMI and vaginal pH. **Sample Size and Power**

Rationale: Cytokine levels are continuous variables and even given this small sample size, should allow for more than adequate power to detect large differences in mean concentrations between pre- and post-treatment groups.

D.3.3. Specific Aims – 3 and 4: To observe for quantitative and qualitative changes in the distribution of OTUs among the bladder and rectal microbiomes. **Hypothesis:** Alterations in the bladder and rectal

microbiomes will occur before and after transvaginal therapy (similar to the changes seen in the vaginal microbiome). These specific aims are exploratory.

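### For the secondary comparison of 20 treated with 5 untreated women, covariates are to be chosen by comparing baseline characteristics; fixing the V1 value as covariate in advance is more precise

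*Combined protocol and SAP*

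**What the plan says.** - **How covariates are found.** D.3.1, Approach: "Baseline characteristics will be recorded and compared among the total cohort to identify covariates for adjusted analyses". Nothing says which characteristics, what kind of comparison, or what result makes a characteristic a covariate.
- **What they are for.** The Aim 1 Biostatistical Analysis Plan says the zero-inflated models "allow analysis of multiple covariates which may vary between treatment and non-treatment groups". This ties the adjusted analyses to treated v untreated women.
- **The biomarker model.** D.3.2, Biostatistical Analysis Plan, describes a linear regression to compare two cohorts: "cytokine concentrations as response, cohort indicator as covariate". It has no V1 term. The next sentence adds that the V1-to-V2 difference in cytokines will be compared between groups by similar methods. VMI and vaginal pH are handled likewise, and D.3.3.1 carries the plans over to bladder and rectum.
- **The groups.** D.2: "Twenty patients will receive the treatment intervention. Five will not receive the treatment intervention". No random allocation is described. D.2 also says the two groups may be compared but that this is not the primary aim. The primary contrast is each woman's own change from V1 to V2 (D.1.1, D.2).

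**The concern.** Choosing covariates by whether they differ at baseline selects on chance imbalance, not on how well they predict the outcome. With 20 and 5 women the comparison also has little ability to detect an imbalance that is really there. The V1 value of the same outcome is usually a strong predictor of its V2 value. Under this rule it enters only if it happens to differ visibly between the groups.

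At stake is the precision of the comparisons between treated and untreated women, and whether two analysts would fit the same model.

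**Working it through.** **1. The plan's own power figure.** D.3.1 states: "With a Type-1 error of 0.05, we estimate with 80% power" and "we can detect an effect size of 0.2 increase (0.4→0.6) in the relative abundance of Lactobacillus spp", "with a treatment sample size of 20 patients", from a baseline of 0.4 with SD 0.3. A paired two-sided t-test with difference 0.2, SD of change 0.3 and n = 20 has noncentrality 0.2/0.3 × √20 = 2.98 on 19 df, and power 80.7%. The smallest n for 80% is 20. An unpaired 20 v 20 t-test would give about 54%. So the stated figure is that of a within-woman contrast, which already uses V1. The covariate rule does not touch it.

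**2. Standard error of a 20 v 5 difference.** √(1/20 + 1/5) = 0.5, so SE = 0.5 × SD.

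**3. Power of a baseline comparison to flag an imbalance.** Assume a two-sided t-test at 0.05; the plan names neither test nor threshold. On 23 df the critical value is 2.07, so an observed difference must exceed 2.07 × 0.5 = 1.03 SD. With noncentrality = true difference/0.5:

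| True baseline difference | Chance it is flagged |
|---|---|
| 0.5 SD | 16% |
| 0.8 SD | 33% |
| 1.0 SD | 48% |

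If the groups are truly balanced on V1, it is selected in about 5% of trials, by definition of the threshold.

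**4. Precision: selection rule v V1 fixed in advance.** Simulation of balanced groups, 20 v 5, screening V1 and eight unrelated traits at p<0.05, with outcome SD 1. The V1–V2 correlation r is an assumption, since the documents give none.

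| r | SE, selection rule | SE, V1 fixed | Variance cut |
|---|---|---|---|
| 0.3 | 0.52 | 0.48 | about 13% |
| 0.5 | 0.52 | 0.45 | about 26% |
| 0.7 | 0.49 | 0.37 | about 45% |

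The cuts come from unrounded SEs; 1 − (ratio of the rounded SEs)² gives 15%, 25% and 43%. The rule does no better than plain V2 without covariates, whose SE is 0.5 by step 2.

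**5. Precision: change score v V1 fixed.** With equal SDs at both visits, the variance per woman is 2(1 − r)SD² for a change score and (1 − r²)SD² with V1 as covariate. The ratio is (1 + r)/2 = 0.65, 0.75, 0.85, a cut of 35%, 25%, 15%. These are large-sample figures. Estimating the slope in 25 women inflates the adjusted variance by about 1/21, so the realised cut is nearer 32%, 21%, 11%.

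**6. What this means for a 0.2 difference in *Lactobacillus* abundance, SD 0.3.** Noncentral t, 23 df (22 with V1), large-sample SEs:

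| r | SE: V2 only / change / with V1 | Power: V2 only / change / with V1 |
|---|---|---|
| 0.3 | 0.150 / 0.177 / 0.143 | 25% / 19% / 27% |
| 0.5 | 0.150 / 0.150 / 0.130 | 25% / 25% / 31% |
| 0.7 | 0.150 / 0.116 / 0.107 | 25% / 38% / 43% |

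At r = 0.5 the difference detectable with 80% power falls from 0.44 to 0.38. Both are about twice the 0.2 the study is designed around.

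**The case against.** The strongest reply is that the 20 v 5 comparison is optional. The five untreated women are there to show that the microbiome is stable, and each treated woman is compared with herself. This stands, and it confines the point to secondary analyses. A reader might infer from the placement of the sentence under Aim 1 that the primary analysis loses power. It does not (step 1).

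Second, the sentence speaks of the total cohort, not of 20 v 5, and gives no test or threshold. Baseline characteristics are undefined, so V1 might be among them. That is fair: the 48% and 5% depend on an assumed p<0.05 t-test, and the plan cannot be said to exclude V1. But the Aim 1 model description points to differences between treated and untreated women. Even if V1 is screened, it enters only when the comparison happens to pick it. A looser threshold does not rescue the rule: screening at p<0.20 with r = 0.5 selected V1 in about 20% of simulated trials, with SE 0.152 on the abundance scale, against about 0.13 with V1 fixed.

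Third, D.3.2 also compares the V1-to-V2 difference between groups, so V1 is not ignored for biomarkers, and the wording about two cohorts could be read as pre v post samples. This also stands. Against the change score the gain is smaller at the higher correlations (step 5), so 45% must not be quoted as the gain over everything planned.

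Fourth, in groups that were not randomised, V1 adjustment is not automatically the less biased choice. If the groups differ stably at baseline, a change score can be unbiased where V1 adjustment is not. That is a reason to show both.

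**Conclusion.** The point holds for the secondary 20 v 5 comparisons of univariate outcomes only. There, choosing covariates from a baseline comparison is a weak rule, and fixing V1 in advance is better: about 13%, 26% or 45% less variance than under the rule, and about 35%, 25% or 15% less than a change score (large-sample), at r = 0.3, 0.5 or 0.7. These figures rest on the assumed threshold, the assumed correlation and equal SDs at both visits.

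Three stronger readings are not supported:
- **That V1 is the only covariate that matters.** No randomisation is described, so other characteristics could confound the comparison.
- **That the rule makes the between-group results biased or falsely significant.** An imbalance in V1 that happens by chance does shift an unadjusted V2 difference in that trial. Averaged over trials with balanced groups there is no bias, and type I error in the simulations under the screening rule was 3.6% to 4.8%.
- **That every between-group analysis should carry V1.** This has no direct meaning for PERMANOVA on Bray-Curtis or UniFrac distances, or for PCoA.

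The practical gain is modest, and the comparison stays underpowered with or without the change.

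**What to change.** Replace the covariate sentence in D.3.1 and the cohort-only regression in D.3.2 with a rule fixed before the data are seen:

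- For any treated v untreated comparison of a univariate outcome (cytokines, VMI, pH, alpha diversity, *Lactobacillus* abundance), model the V2 value on cohort plus the V1 value of the same outcome.
- Allow at most a very short list of further covariates, named in advance and chosen because they are expected to predict the outcome.
- Describe baseline characteristics by group, but do not use their comparison to select covariates.
- Label the 20 v 5 comparison descriptive, because allocation is not described as random, and report the change-score result beside it as a sensitivity analysis.

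The cost is a change of wording in the analysis plan; the V1 samples are already scheduled. V1 and perhaps one more covariate use one or two degrees of freedom in 25 women. The change does not make the comparison confirmatory: at r = 0.5, power for a 0.2 difference goes from about 25% to about 31%.

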Assessing the interrelationships of these microbiomes and local inflammatory biomarkers is crucial to understanding how pathologic or therapeutic changes in these markers affect the other microbiome niches. Given that the microbiomes of these three environments are conceivably modifiable, the understanding of the correlative relationship between the microbiomes and inflammatory biomarkers as well as objective improvement of the vagina can provide important clarity and guidance for future research and potential therapies. Results from this study will also serve to guide estimations of power and necessary cohort numbers. Currently the baseline and post treatment compositions of these microbiomes are unclear in our study population of interest and this pilot study will help to define that. If our hypotheses are confirmed, future studies from samples collected in this pilot study will allow us to investigate the relationships of rectal, urinary, and vaginal metabolites in VVA and its associated physiologic and inflammatory changes. Furthermore, alternative prophylactic uses of vaginal estrogen for prevention of lower genitourinary tract conditions may also be explored.

D. METHODS

D.1 Study Population

D.1.1. Cohort Identification: Postmenopausal women ≥ 55 years old with clinically diagnosed vulvovaginal atrophy. Twenty volunteer patients will be placed in the intervention arm. The primary aim is to compare the change in the data points of interest over the eight week study period in a pre- and post-treatment comparison manner. The five patients meeting the same inclusion/exclusion criteria will serve as a control cohort, not to receive treatment, and are included in this study to demonstrate microbiome stability across the eight week time period. We anticipate interest and participation in this study from planned advertisements and women seen in the UAB Urogynecology and Women's Reproductive Health Clinics.

Figure 1. Flow Diagram of Enrollment and Study Design

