Microbiome Analysis Statement of Rigor: Several quality controls are performed: 1) removing sequences with low quality scores, those matching human databases and low-duplicates and 2) merging paired reads and discarding sequences with substantial differences. Results from the UAB Microbiome Resource pipeline showed that duplicate samples had significant co-clustering on Principal Coordinate Analysis (PCoA) plots. Using 16S rRNA gene and whole genome DNA sequences from 20 known species, we are able to correctly identify organisms with unique 16S rRNA V4 genes to the genus and even species level and predict genetic pathways. **Sample Size and Power Rationale:** Our sample size calculation is based upon our primary aim to evaluate the expected quantitative change in relative abundance of Lactobacillus genus and spp among the community composition of bacteria in the vagina. There's an abundance of research reporting the normalization of the vagina by objective measures by various routes of estrogen therapy, specifically by serving to facilitate the increase of the relative Lactobacillus presence. However, it is difficult to define how much of an increase in Lactobacillus is needed to be clinically relevant. As previously stated there is no previous study by which to reference in predicting what the expected change in Lactobacillus may be in the setting of vaginal estrogen therapy. A previous study (22) has compared a cohort of atrophic vaginitis (AV) patients who received low dose oral estrogen therapy to a healthy control (not receiving therapy); all patients were postmenopausal meeting strict criteria. Vaginal sampling took place at baseline, two weeks,

Table 1. Description of Sample Numbers and Locations.

SAMPLE LOCATION	Pre-Treatment	Post-Treatment
VAGINA		
Inflammatory Biomarkers	25	25
Microbiome	25	25
BLADDER		
Inflammatory Biomarkers	25	25
Microbiome	25	25
RECTUM		
Inflammatory Biomarkers	25	25
Microbiome	25	25

and at four weeks after treatment initiation. Among the AV group the relative abundance of Lactobacillus pretreatment was 0.112 ± 0.164 . At 4 weeks of oral estrogen therapy the Lactobacillus abundance rose dramatically to 0.71 ± 0.375 . The baseline abundance among the “healthy” untreated postmenopausal cohort was 0.532 ± 0.403 and virtually without change over the four week period.

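### The design compares each woman with herself, but Table 2 names an independent-samples test and no pairing is stated for the other pre/post analyses, including the primary Lactobacillus models

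*Combined protocol and SAP*

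**What the plan says.** Three places set a within-woman comparison. Section D.1.1 gives the primary aim as to "compare the change in the data points of interest over the eight week study period". Section D.2 states: "The intention of this study is for each of the subjects to serve as her own control". The Approach in D.3.1 plans "to compare samples from each subject prior to initiation of vaginal estrogen cream and then again after eight weeks of therapy", with 20 treated women at each visit.

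The analysis text does not carry this through:

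- **Community-level analysis (D.3.1, Table 2).** It is introduced as a way to "investigate the overall microbiome differences between the pre-treatment and post-treatments groups". For alpha diversity it lists "t-tests, Mann-Whitney U". For beta diversity it lists PERMANOVA or a Dirichlet-multinomial Wald-type test, without restriction by woman.
- **Taxa-specific models (D.3.1).** These cover Lactobacillus. They are zero-inflated negative binomial, Gaussian and beta regressions with covariates. No random effect or other woman-level term is mentioned, and none is ruled out.
- **Aim 2 (D.3.2).** Cytokines and VMI are compared before and after by a t-test or a non-parametric test, with pairing not stated. The regressions that use both visits list a visit indicator and its interaction with the covariate, but nothing for the woman.
- **Aims 3 and 4 (D.3.3.1).** These follow the plans of Aims 1 and 2.

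The power statement in D.3.1 claims 80% for a rise from 0.4 to 0.6 with 20 treated women at a type I error of 0.05. The only SD offered for this cohort is in "we expect the relative abundance of Lactobacillus spp to be approximately 0.4 ± 0.3". The test, its sidedness, the SD of change and the correlation between visits are not given.

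**The concern.** Two samples from one woman are not independent. A test that treats them as if they were leaves the between-woman variance in the error of the before/after contrast. When the visits are positively correlated, the standard error is too large, the null rejection rate falls below 5%, and power is lost. With 20 women there is little to spare.

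The study tests a stated hypothesis of a significant increase in Lactobacillus. It is also meant to guide the sizing of later studies, and an unpaired analysis does not yield the SD of change that such sizing needs. Leaving pairing unstated also lets the choice be made after the data are seen.

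**Working it through.** **Inputs.** From D.3.1: n = 20 treated women, rise δ = 0.2, type I error 0.05, SD 0.3. Assumed here: two-sided testing, the same SD of 0.3 at both visits, and a correlation ρ between visits of 0, 0.3, 0.5 or 0.7. The documents give no ρ.

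**Step 1: reproduce the 80%.** For a paired t-test the noncentrality is δ/(SD of change/√n). Using 0.3 as the SD of change gives 0.2/(0.3/√20) = 2.98 on 19 df, and power 80.7%. Twenty is the smallest n that reaches 80%; 19 gives 78.5%. A one-sample test against a fixed 0.4 with SD 0.3 is the same formula and also gives 80.7%, so the calculation actually used cannot be confirmed. An unpaired test of 20 against 20 with SD 0.3 has noncentrality 0.2/(0.3·√(2/20)) = 2.11 on 38 df, and power 53.8%.

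**Step 2: what 80% requires.** The largest SD of change that gives 80% is 0.303 (0.347 if one-sided). If 0.3 is the SD at each visit, the SD of change is 0.3·√(2(1−ρ)). Setting this to 0.303 gives ρ = 1 − 0.303²/(2·0.3²) = 0.49.

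**Step 3: paired against unpaired.** Paired t figures are from the noncentral t distribution. The rest are simulated with normal data (20,000 replicates; 4,000 for signed-rank).

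| Assumed ρ | 0 | 0.3 | 0.5 | 0.7 |
|---|---|---|---|---|
| SD of change | 0.424 | 0.355 | 0.300 | 0.232 |
| Paired t, power | 51.6% | 66.7% | 80.7% | 95.4% |
| Women needed for 80%, paired | 38 | 27 | 20 | 13 |
| Unpaired t, power | 53.9% | 54.5% | 54.9% | 57.1% |
| Signed-rank, power | 49.5% | 63.9% | 78.8% | 94.9% |
| Mann-Whitney U, power | 51.7% | 51.7% | 52.2% | 54.3% |
| Unpaired t, type I error | 5.0% | 2.1% | 0.8% | 0.1% |

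If the rise is 0.3 instead of 0.2, unpaired power is 87% by formula.

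**Step 4: a planned model type.** A one-part Gaussian model on arcsine-square-root abundance was simulated (4,000 replicates; realised correlations about 0, 0.28, 0.47 and 0.66). Power was 54%, 58%, 58% and 58% without a woman term, and 52%, 69%, 82% and 96% with one. With assumed zeros in 20% of samples at the first visit and 10% at the second, it was 49%, 49%, 52% and 52% against 47%, 60%, 75% and 90%. The zero-inflated negative binomial and beta models were not simulated.

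**Step 5: Aim 2 regressions as written.** With within-woman correlation of 0.3, 0.5 and 0.7 in both variables, the interaction test rejects a true null 4.2%, 2.7% and 0.8% of the time. The single-visit slope stays near nominal (4.9%, 5.2%, 5.0%).

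**Step 6: the SDs of the cited cohort.** D.3.1 reports "Among the AV group the relative abundance of Lactobacillus pretreatment was 0.112 ± 0.164" and "At 4 weeks of oral estrogen therapy the Lactobacillus abundance rose dramatically to 0.71 ± 0.375". The SD of change is √(0.164² + 0.375² − 2ρ·0.164·0.375), which is 0.409, 0.361, 0.326 and 0.285 over the same ρ. Paired power for a rise of 0.2 is then 55%, 65%, 74% and 84%, and 80% needs ρ of about 0.62. With that cohort's own rise (0.71 − 0.112 = 0.598), even an unpaired test has power above 99.9%. The SDs therefore bear on the 0.2 claim, not on whether a rise of that size would be detected.

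**The case against.** The text signals pairing repeatedly, and the sample size fits it: 20 is exactly the smallest n that gives 80% for a two-sided paired t-test with SD 0.3, while an unpaired test gives 54%. The t-tests, PERMANOVA and the Aim 2 tests can all be run paired. D.3.2 speaks of correlating changes with changes and of comparing the change in cytokines between groups. Only Mann-Whitney U is positively mismatched, and it concerns alpha diversity, not the primary outcome. The loss is conservative, depends on a correlation that nobody has stated, and arises in a pilot whose Aims 3 and 4 are exploratory.

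Most of this stands, and it limits the point. For Lactobacillus the fault is an omission, not a wrong instruction. The two change-based items in D.3.2 do not close it, because neither supplies a before/after test for the primary outcome.

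A reader might infer that the primary outcome will be analysed unpaired, or that true power is 54% and the 80% is an error. The documents support neither: pairing is left open, and the 80% follows if 0.3 is the SD of change. A reader might also infer inflated false positives. With positive correlation the opposite holds.

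**Conclusion.** The point holds as a mismatch in one named test and an omission elsewhere. Mann-Whitney U does not suit the before/after alpha-diversity comparison. Pairing or a woman-level term is unstated for the Lactobacillus models, PERMANOVA, and the Aim 2 tests and two-visit regressions.

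If the analyses are run unpaired, the cost at an assumed correlation of 0.5 is about 81% power falling to 54%. There is no cost at zero correlation, and it matters less if the true rise exceeds 0.2. These sizes rest on assumed correlations, an SD of 0.3 at both visits and two-sided testing. For the zero-inflated negative binomial and beta models the size of the loss is inferred, not computed.

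The stated 80% is an undocumented assumption, not a demonstrated error. Pairing alone does not secure it: at a correlation of 0.3 the paired test has 67%.

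Severity: should be fixed.

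**What to change.** - Replace Mann-Whitney U in Table 2 with the Wilcoxon signed-rank test. For Table 2 alpha diversity and Aim 2, specify paired t-tests or signed-rank tests on visit 2 minus visit 1 in the 20 treated women.
- Restrict PERMANOVA permutations to within woman. Do not use the independent-groups form of the Dirichlet-multinomial Wald test for the before/after contrast.
- Make a paired analysis of Lactobacillus abundance, or a model with a woman-level random intercept, the primary analysis. Add a woman-level term to every model that uses both visits.
- Use cluster-robust errors only with a small-sample correction and a t reference. Uncorrected, with 20 women and a normal reference, a simple before/after contrast has type I error 2·P(t₁₉ > 1.96·√(19/20)), about 7.1%.
- State the test, the sidedness and the SD of change behind the 80%, and show power over a range of correlations.

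The cost is SAP rewording and minor coding, and possibly a different package, since the documents do not show whether the named one fits a woman-level term. No new patients or samples are needed. The stated power may become less favourable.

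### Table 2 leaves the test of overall community composition open, and one permitted option, the Dirichlet-multinomial Wald test, becomes severely conservative on a species- or OTU-level table if referred to chi-square

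*Combined protocol and SAP*

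**What the plan says.** The beta-diversity row of Table 2 (section D.3.1, Biostatistical Analysis Plan) gives the comparison of overall composition as "PERMANOVA or Dirichlet-multinomial distribution with Wald-type test", in a column for two-group comparisons. The plan does not say how to choose between the two, at what taxonomic rank the table is built, how many taxa enter, whether rare taxa are filtered, or what reference distribution the Wald statistic takes.

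Three other places bear on this:

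- Section D.2 describes a paired design; the intention is "for each of the subjects to serve as her own control". The D.3.1 Approach gives "Treatment Group V1 = 20 vs. V2 = 20".
- The aims speak of OTU distributions, and the D.3.1 Approach aims for species-level resolution with DADA2. The paragraph after Table 2 describes the data as "compositional counts/proportions, varying total sequence reads across samples, over-dispersion" and adds zero-inflation.
- The sample-size paragraph concerns Lactobacillus only: "we expect the relative abundance of Lactobacillus spp to be approximately 0.4 ± 0.3", and "we estimate with 80% power that we can detect an effect size of 0.2 increase" "in the relative abundance of Lactobacillus spp with a treatment sample size of 20 patients". Individual taxa are assigned to separate taxa-specific models.

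Section D.3.3.1 carries the Aim 1 analysis plan over to bladder and rectum.

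**The concern.** The two options in the row behave very differently on these data. PERMANOVA takes its p-value from permutation, so many rare taxa do not by themselves distort its error rate. The Dirichlet-multinomial Wald statistic is usually referred to a chi-square with one degree of freedom fewer than the number of taxa. Each added rare taxon raises the critical value. With 20 samples per visit and strong over-dispersion, the statistic does not grow to match.

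If that option were used on an uncollapsed table, a null result would say little about whether the community had changed. Leaving the choice open also allows it to be made after the data are seen. Neither option, as written, uses the pairing.

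**Working it through.** **Inputs from the plan.** 20 treated women sampled at two visits; Lactobacillus 0.4 to 0.6; SD 0.3; "With a Type-1 error of 0.05" (sidedness not stated; two-sided used here).

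**Inputs assumed.** Number of taxa K from 2 to 100; read depth 5,000 to 50,000; non-Lactobacillus taxa mostly skewed and shrinking in proportion as Lactobacillus rises; pre-post correlation of Lactobacillus either 0 or about 0.4-0.5.

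**Step 1: the plan's own figure.** A paired t-test with n = 20, change 0.2 and SD of change 0.3 has noncentrality 0.2/(0.3/√20) = 2.98 and power 80.7%. The stated 80% therefore reproduces. If 0.3 is the SD at each visit, the SD of the change is 0.3 × √(2(1 − ρ)), which equals 0.3 only when ρ = 0.5. An unpaired 20 v 20 t-test gives 54%. The plan's sizing thus matches an analysis that uses the pairing.

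**Step 2: the Wald test in large-sample theory.** Over-dispersion implied by the plan: θ = 0.3²/(0.4 × 0.6) = 0.375. With high, equal depth, the statistic is W = (n/2) × Σ(difference²/mean proportion)/θ. For 0.4 to 0.6 the sum is 0.2²/0.5 + 0.2²/0.5 = 0.16 at any K. The noncentrality is 10 × 0.16/0.375 = 4.27. It stays fixed while the degrees of freedom, K − 1, grow.

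**Step 3: simulation of the same test with chi-square p-values.** The simulated power range covers uncorrelated and correlated visits. Null rejection is for uncorrelated visits.

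| Taxa K | Chi-square 5% point | Large-sample power | Simulated power | Null rejection |
|---|---|---|---|---|
| 2 | 3.8 | 54% | 46-55% | 4-6% |
| 5 | 9.5 | 34% | 15-33% | about 4% |
| 10 | 16.9 | 24% | 3-25% | 1-2% |
| 20 | 30.1 | 17% | 0-10% | 0-0.2% |
| 50 | 66.3 | 12% | 0% | 0% |

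The low end at 5 and 10 taxa comes from correlated visits: the test treats the samples as independent and so overstates the variance of the change. In even communities of 4 to 20 taxa the coded test rejected 4-6% of the time under the null, so the collapse is not a coding fault. Monte Carlo error is about 2 percentage points.

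**Step 4: a bound that needs no simulation.** With equal depth, the sum in W cannot exceed 4 (no taxa shared between visits), so W cannot exceed 2n/θ = 40/0.375 = 106.7. The chi-square 5% point on 85 degrees of freedom is 107.5. At this over-dispersion, rejection is impossible from K = 86 upward.

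**Step 5: PERMANOVA on Bray-Curtis, same kind of data.** Uncorrelated visits: 37-53%. Correlated visits: about 22-51% with free permutation and about 56-79% with permutation within woman. Monte Carlo error is about 4 points.

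**Step 6: does calibration rescue the Wald statistic?** Partly. With its size corrected to 5%, power was about 6-32% for K = 20 to 100 in one set of runs; another set using permutation p-values gave 43-47%. Collapsing to nine taxa plus an 'other' category gave 16-20% with the chi-square and uncorrelated visits, and about 23-38% after size correction.

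**The case against.** The strongest reply is that the plan fixes none of the things that make the test fail. It gives no taxon count and no filter, and it names no reference distribution; permutation calibration is not excluded. The over-dispersion and zero-inflation it mentions introduce the taxa-specific models, not Table 2. That stands. A reader might infer that 20 v 20 over-dispersed samples alone leave the Wald test with almost no power. The documents do not support this: at 2 to 5 taxa power is about 15-55%. At an assumed SD of 0.2 with less dispersed other taxa, it is 53% with 10 taxa and 24% with 20.

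A reader might also infer that the stated 80% power is undermined. It is not: that figure belongs to vaginal Lactobacillus relative abundance, which has its own models, and the plan claims no power for the community-level comparison. Nor can the result be carried to bladder and rectum as a number. The 0.4 to 0.6 shift is vaginal, the plan gives no Lactobacillus mean, SD or expected change for the other two sites, and it calls those aims exploratory.

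Finally, simply striking out the Wald option would not be enough. Freely permuted PERMANOVA ignores the pairing and can be left with about 22-51% power.

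What remains is that the plan aims for OTU and species-level description, and nothing in it suggests a table of only a few taxa. On a larger table with the usual chi-square, the permitted test does not hold its nominal level.

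**Conclusion.** The point holds in conditional form. Table 2 leaves the test, the taxa filter and the handling of pairing unspecified. One permitted analysis, the Dirichlet-multinomial Wald test with a chi-square p-value, is severely conservative on a species- or OTU-level table of 20 pre and 20 post samples. At the plan's SD of 0.3, its power for the 0.4 to 0.6 shift is at most about 10% at 20 taxa and nil at 50, and it almost never rejects under the null from about 20 taxa.

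These figures rest on the assumed number of taxa, the shape of the non-Lactobacillus community, read depth and pre-post correlation, and on the chi-square being used. They apply to the vaginal pre-post comparison only.

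**What to change.** In the beta-diversity row of Table 2, name PERMANOVA with permutations restricted within woman as the single test of overall pre- versus post-treatment composition. State the taxonomic rank and any rare-taxon filter before the data are seen.

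If a Dirichlet-multinomial Wald statistic is kept, make it a sensitivity analysis on a pre-specified collapsed set of taxa, with its p-value from within-woman permutation and not from the chi-square.

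The cost is analysis-plan wording and slightly more computation. No new samples or data are needed.
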